Rationale / context	
In France, the prevalence of undernutrition in hospitalized patients varies from 30 to 50%. Undernutrition is strongly associated with a decrease in the patient's functional abilities and an increase in morbidity and mortality and healthcare expenses. In 2019, the Global Leadership Initiative on Malnutrition (GLIM) published an international consensus report on diagnostic criteria for undernutrition (1). The diagnostic criteria are numerous, and include etiological criteria such as reduced food intake; an inflammatory setting; symptoms such as anorexia, fatigue; phenotypic criteria such as weight loss, body mass index (BMI), fat to lean mass ratio, fluid retention, and muscle function.
 
Muscle mass is described as a major diagnostic criterion, since it is on the one hand a direct indicator of protein catabolism related to undernutrition, but also a reflection of functional impairment in the patient, as it is directly associated with functional capacities, autonomy and prognosis. Ultrasound is a reproducible method of muscle assessment. It allows the evaluation of muscle thickness or cross-sectional area of a muscle, the reduction of which, a marker of atrophy, is strongly correlated to its loss of strength and to reference measurements. In addition, ultrasound can be used to assess muscle quality, particularly by evaluating the echogenicity of the muscle. The echogenicity increases when the muscle is altered, linked to the presence of fatty infiltrate and fibrous tissue. The use of ultrasound in the evaluation of the patient's nutritional status, as a tool for assessing muscle function, is developing in the ICU and is associated with an increase in the patient's comorbidities. Studies remain limited to a few patient populations, do not report clear cut-off values to define muscle pathological status, and require more precise definition of ultrasound measurement protocols. We hypothesize that muscle ultrasound is reliable and valid in the evaluation of muscle function during the screening of undernutrition in a population of patients hospitalized in diabetology-obesity, pneumology, oncology and gastro-nutrition, under 70 years old.

Main Objective	To evaluate the reliability and validity of muscle ultrasound in the context of screening for undernutrition in hospitalized patients
Secondary objectives	
 - Evaluate the correlation of muscle ultrasound with standard measures of muscle function; - Compare the diagnostic ability of muscle function assessment tools on undernutrition; - Evaluate the association of muscle ultrasound measurements with patient morbidity and mortality: 
 • Length of hospitalization; • Mortality rate; • Autonomy at discharge.

Research Diagram	Prospective, monocentric, interventional cohort study with minimal risks and constraints falling within the scope of article L.1121-1 of the Public Health Code.
Inclusion criteria	
 - Admitted in short stay and follow-up care and rehabilitation of diabetes-obesity, pneumology, oncology and gastro-nutrition; - Age between 18 and 70 years at inclusion; - Affiliation with a social security system or beneficiary of such a system ; - Oral, free, informed and express consent of the patient or his/her family member.
Non-inclusion criteria	
 - Impossibility of performing bioelectrical impedanceometry ; - Patient refusal to participate in the study; - Pregnancy (a pregnancy test should be performed if in doubt); - Breastfeeding woman; - Person subject to a safeguard of justice measure ; - Patient under guardianship or curatorship; - Patient in care limitation; - Sampling in the ineligible study group.
Primary endpoint	The primary endpoint is the diagnostic accuracy (sensitivity, specificity) of muscle ultrasound in undernutrition in patients hospitalized in short-stay and follow-up care and rehabilitation of diabetes-obesity, pneumology, oncology and gastro-nutrition.
Secondary endpoints	
Secondary endpoints will be:
 
 - Correlation measurements of muscle ultrasound with: 
 • Bioelectrical impedanceometry; • Handgrip; • Walking speed. - Comparison of the diagnostic accuracy in undernutrition of muscle ultrasound with those of : 
 • Bioelectrical impedancemetry; • Handgrip; • Walking speed. - Measure of association of muscle ultrasound measures with patient morbidity and mortality: 
 • Length of hospitalization (days); • Mortality: proportion and date of occurrence of death among patients included during hospitalization; 
Autonomy at discharge: Activities Daily Living (ADL) score

Comparison group	Patients hospitalized in short stay and follow-up care and rehabilitation of diabetes-obesity, pneumology, oncology and gastro-nutrition.
Number of subjects needed	118
Expected number of centers	1
Duration of the research	21 months
Statistical analysis of the data	
Inter and intra-examiner reliability will be assessed by calculating the intra-class correlation coefficients. Validity will be assessed by calculating the areas under the ROC curve (Receiver Operating Characteristics) and the calculation of sensitivities, specificities, positive and negative predictive values.
 
The gold standard test for diagnosing impaired muscle function is bioelectrical impedance.
 
Descriptive statistics will use the usual statistical tests after verification of the distribution of the variables (Chi2 or Fisher's test, t-test, anova or their non-parametric equivalents Wilcoxon and Kruskal-Wallis tests). The variables will be compared by the appropriate tests according to the type of variables (quantitative or qualitative) and their distribution.

Expected benefits	The results of this study will make it possible to verify whether ultrasound is a reliable and valid tool in the evaluation of peripheral muscle function in the context of screening for undernutrition. On the other hand, they will allow us to propose threshold values for the alteration of muscle function and to provide information on the ultrasound characteristics of the muscle in the undernourished patient and their association with the prognosis of the patient. The different tools could lead to a different estimation of the reduction of muscle mass and therefore a different prevalence of undernutrition. The results of our study will help to evaluate this and to guide professionals in the choice of tools to evaluate muscle function.
Source of funding	Forcilles Hospital-Cognacq-Jay Foundation
Independent Supervisory Committee planned	No

TABLE OF CONTENTS

PROTOCOL VERSION HISTORY.....	3
RESEARCH SUMMARY.....	4
TABLE OF CONTENTS.....	7
1 RATIONALE FOR THE RESEARCH	9
1.1 EPIDEMIOLOGY AND MORBIDITY OF UNDERNUTRITION	9
1.2 INTERNATIONAL CONSENSUS ON THE DEFINITION OF UNDERNUTRITION	9
1.3 ROLES OF PROFESSIONALS IN SCREENING FOR UNDERNUTRITION	11
1.4 ASSESSMENT OF MUSCLE FUNCTION	11
1.5 MUSCLE ULTRASOUND AND UNDERNUTRITION	12
1.6 RESEARCH HYPOTHESIS	13
2 ORIGINALITY OF THE RESEARCH	13
3 OBJECTIVE	13
3.1 MAIN OBJECTIVE	13
3.2 SECONDARY OBJECTIVES.....	13
4 JUDGING CRITERIA.....	14

1.1 Epidemiology and morbidity of undernutrition

Undernutrition, whether related to disease, poverty, hunger, war or natural disasters, affects more than one billion people worldwide (1). In France, an empirical estimate suggests a prevalence of undernutrition among hospitalized patients of about 2 million (2) or 30 to 50% (3). It should be noted that undernutrition is very common in and out of hospital. It is widely accepted that undernutrition can be caused by a deficit in nutrient intake or malabsorption. However, it is now known that the inflammatory state present during illness is associated with undernutrition (1). The inflammatory state promotes anorexia and decreased intake but also increases basal metabolic rate and muscle catabolism. Undernutrition is marked by a decrease in all markers of muscle mass (1). It is thus strongly associated with a decrease in the patient's functional capacities and an increase in morbidity and mortality and in health care costs (1,4-6).

1.2 International consensus on the definition of undernutrition

In 2019, the Global Leadership Initiative on Malnutrition (GLIM) published an international consensus report on diagnostic criteria for undernutrition (1). The diagnostic criteria are numerous, and include etiological criteria such as reduced food intake; an inflammatory context; symptoms such as anorexia, fatigue; phenotypic criteria such as weight loss, body mass index (BMI), fat to lean mass ratio, fluid retention, and muscle function. GLIM has chosen to select the most relevant criteria among the etiological and phenotypic criteria:

- Etiological criteria: reduced food intake and inflammatory state of the patient;
- Phenotypic criteria: weight loss, BMI, and reduced muscle mass. The presence of at least one etiological criterion and one phenotypic criterion is mandatory to make the diagnosis of undernutrition (Table 1).

Table 1: Diagnostic criteria for undernutrition

Phenotypic criteria			Etiological criteria	
Weight loss (%)	Low BMI (kg/m ²) ²	Reduction in muscle mass	Reduction of food intake or absorption	Inflammatory situation
> 5% in the last 6 months or > 10% beyond 6 months	< 20	Reduction evaluated by a validated measurement technique*.	≤ 50% of food intake > 1 week or any reduction > 2 weeks, or any gastrointestinal pathologies or symptoms impacting assimilation or absorption	Acute pathologies or certain chronic or malignant pathologies
≥ 5% in 1 month or ≥ 10% in 6 months or loss ≥ 10% from usual weight prior to start of the disease	< 18,5	Quantified Reduction* * (QR)	Same as	Same as

* Suggested methods of measuring muscle mass: Dual X-ray Absorptiometry (DEXA); bioelectrical impedance; CT or MRI. In the absence of these tools, anthropometric measurements such as arm or leg circumference can be used. Grip strength measurement is considered a complementary measure. The threshold values are those of Cruz et al (7).

** Methods of measuring muscle mass proposed by the HAS:

Muscle mass is described as a major diagnostic criterion, since it is on the one hand a direct indicator of protein catabolism related to undernutrition, but also a reflection of functional impairment in the patient, as it is directly associated with functional capacities, autonomy and prognosis (1). Different measurement tools are suggested, such as bioelectrical impedance, ultrasound or magnetic resonance imaging, leaving the choice of tool to the clinicians, depending on experience and local resources. Handgrip measurement is considered a complementary measure.

GLIM recommends an assessment of the risk of undernutrition, using validated questionnaires such as the NRS (Nutritional Risk Screening) or the MNA-SF (Mini Nutritional Assessment-Short Form). The degree of severity of undernutrition is only assessed on the basis of phenotypic criteria.

The severity of undernutrition can then be determined (Table 2).

Table 2: Classification of the severity of undernutrition

Moderate undernutrition	Severe undernutrition

 • BMI < 20 kg/m² • Weight loss of 5-10% in the last 6 months or 10-20% beyond 6 months • Mild to moderate reduction in muscle mass 	
 • BMI < 18.5 kg/m² • Weight loss of >10% in the last 6 months or >20% beyond 6 months • Severe reduction in muscle mass

 • 17 < BMI < 18.5 kg/m² • Weight loss \geq 5% in 1 month or \geq 10% in 6 months or loss \geq 10% from usual weight before onset of illness • Measurement of albumin by immuno-electrometry or immunoturbidimetry > 30 g/L and < 35 g/L. 	
 • BMI < 17 kg/m² • Weight loss \geq 10% in 1 month or \geq 15% in 6 months or loss \geq 15% from usual weight before onset of disease • Measurement of albumin levels by immuno-electrometry or immunoturbidimetry < 30 g/L

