5.1 Inclusion criteria

Patients with the following criteria will be included:

- Admitted in short stay and follow-up care and rehabilitation of diabetology-obesity, pneumology, oncology and gastro-nutrition;
- Age between 18 and 70 years at inclusion;
- Affiliation with a social security system or beneficiary of such a system ;
- Oral, free, informed and express consent of the patient or his/her family member.

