7.3 Definition of undernutrition

Undernutrition is defined according to the GLIM diagnostic method:

Phenotypic criteria			Etiological criteria	
Weight loss (%)	Low BMI (kg/m ²)	Reduction in muscle mass	Reduction of food intake or absorption	Inflammatory situation
> 5% in the last 6 months or > 10% beyond 6 months	< 20	Reduction evaluated by a validated measurement technique*.	≤ 50% of food intake > 1 week or any reduction > 2 weeks, or any gastrointestinal pathologies or symptoms impacting assimilation or absorption	Acute pathologies or certain chronic or malignant pathologies

The diagnosis of undernutrition is positive if an etiological and a phenotypic criterion are present. This assessment will be preceded by a MNA-SF ([Appendix 4](#)). The methods for measuring the reduction in muscle mass are described in section "**7.2.4. Measurement of muscle function**".

Among patients with undernutrition, severe undernutrition is defined as:

Moderate undernutrition	Severe undernutrition

 • BMI < 20 kg/m² • Weight loss of 5-10% in the last 6 months or 10-20% after 6 months • Mild to moderate reduction in muscle mass 	
 • BMI < 18.5 kg/m² • Weight loss of >10% in the last 6 months or >20% beyond 6 months • Severe reduction in muscle mass

The prevalence of undernutrition was defined as the proportion of patients with moderate and/or severe undernutrition among the patients included in the study.

8 Evaluation procedure added by the research

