9.1.2 Sampling of the population

A potential of 94 patients per month eligible for this study are admitted in short stay and follow-up care and rehabilitation of diabetes-obesity, pneumology, oncology and gastro-nutrition. We anticipate a maximum inclusion of 6 patients per month for logistical reasons.

In order to obtain a representative sample of this patient population in the study, we will sample the patient population upon admission, if he/she meets the eligibility criteria and before the patient is informed and consented. The patient will be randomly assigned to either the eligible or ineligible group. Patients in the ineligible group will not be included in the study, but the number of these patients will be collected.

Patients will be sampled via a centralized random drawing system available via the internet, according to a pre-established list. This list will be programmed in advance by the study statistician. The sampling will be stratified on the care service, and unbalanced using random blocks in order to obtain a number of eligible patients of 10 per month (in order to take into account possible refusals of participation). Only the hospital's research coordinator will know the sampling list.

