9.2 Inclusion visit

The inclusion visit will take place within 48 hours of the patient's or family member's consent to participate in the study. The following data will be collected:

- Age, weight, height, BMI, gender (male/female);
- Hospitalization Service;
- Reason for hospitalization;
- Background;
- Reduced food intake or absorption;
- Inflammatory situation;
- Biological markers (albumin, pre-albumin, CRP) if applicable;
- Nutritional data (weight evolution over the last months, theoretical needs, ingestas) ;
- Mini-Nutritional Assessment Short-Form (MNA-SF);
- Autonomy Score (Katz ADL);
- Ultrasound measurements;
- Bioelectrical impedance data;
- Grip force (Handgrip);
- Walking speed.

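### The undernutrition label in section 7.3 does not ask whether weight loss or reduced intake was intended, so deliberate weight loss can count as a case in the secondary comparison of tools

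*Combined protocol and SAP*

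**What the plan says.** Section 7.3 carries the consensus criteria of section 1.2, Table 1, into the study. The weight-loss criterion is "> 5% in the last 6 months or > 10% beyond 6 months". The intake criterion is "≤ 50% of food intake > 1 week or any reduction > 2 weeks", with digestive conditions that affect absorption as a further alternative. The inflammatory criterion is met by acute disease and by certain chronic or malignant diseases. The decision rule is: "The diagnosis of undernutrition is positive if an etiological and a phenotypic criterion are present". No cell mentions whether the loss or the reduction was intended.

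The population in 5.1 is "Admitted in short stay and follow-up care and rehabilitation of diabetology-obesity, pneumology, oncology and gastro-nutrition", and 9.1.2 adds: "The sampling will be stratified on the care service". The share of each service is not given.

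For weight and intake, section 9.2 collects "Nutritional data (weight evolution over the last months, theoretical needs, ingestas". It has no item on intent. It also lists BMI, service, reason for hospitalization, medical background and the MNA-SF. On that score 7.3 says only: "This assessment will be preceded by a MNA-SF".

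The label has two uses: the prevalence defined in 7.3, and the comparison of handgrip, gait speed, impedance and ultrasound by ROC curves for undernutrition (4.2, 10.5.2). The primary accuracy analysis uses impedance thresholds as its reference (4.1, 10.4).

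**The concern.** Take a patient of the diabetology-obesity service who lost 8% of body weight in six months on a chosen diet, eating less for more than two weeks. That patient meets both halves of the rule in 7.3 whatever the state of the muscle. Section 1.1 describes undernutrition as marked by a fall in all markers of muscle mass, so a case with preserved muscle runs against the idea that the tools are being tested on.

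Such cases can only raise the prevalence. In the ROC comparison they sit among the positives with the muscle values of negatives, which lowers the AUC of each tool and narrows the differences between tools. The protocol says its results should guide professionals in choosing a tool (section 11), so a diluted comparison matters there.

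**Working it through.** **1. Does the sample size depend on this label?** Section 10.1 gives 118 from ICC values ρ1 = 0.80 and ρ0 = 0.70, k = 2, α = 0.05 and power 80%. With θ = ρ/(1−ρ), θ0 = 2.333 and θ1 = 4. Then C0 = (1 + 2×2.333)/(1 + 2×4) = 0.630, and n = 1 + 2(1.645 + 0.842)²×2 / [(ln 0.630)²×1] = 116.6, so 117 with one-sided α. This agrees with 118 to within one patient. Undernutrition prevalence does not enter. The validity calculation uses the prevalence of muscle impairment, not of undernutrition.

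**2. Does the MNA-SF step remove these patients?** Take a patient with BMI above 23, no loss of appetite and full marks elsewhere (Appendix 4, items A to F).
- Loss above 3 kg in three months: 2+0+2+2+2+3 = 11, at risk.
- Loss of 1 to 3 kg: 2+2+2+2+2+3 = 13, satisfactory.

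The weight item asks nothing about intent, and the rule in 7.3 does not include the score. At most it is a partial filter.

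**3. How many labels could be affected?** From the documents: N = 118, and a background prevalence of 30 to 50% (section 1.1). Everything else is assumed.

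*Set A.* Service share s = 10 to 40%; share q = 10 to 50% of the service's truly non-undernourished patients meet the rule through intended loss; true prevalence p = 30 to 50%. Affected patients = 118 × s × q × (1−p).
- Low: 118 × 0.10 × 0.10 × 0.50 = 0.6.
- High: 118 × 0.40 × 0.50 × 0.70 = 16.5.

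*Set B.* p = 40%, so 47.2 true cases; f = 20 to 50% of all the service's patients have intended loss as their only phenotypic criterion. Affected patients = 118 × s × f.
- s = 25%: 5.9 to 14.8 patients, or +5 to +12.5 points of prevalence.
- s = 15 to 40%: 118 × 0.15 × 0.20 = 3.5, up to 118 × 0.40 × 0.50 = 23.6.

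**4. Effect on the AUC if affected patients have the muscle values of non-cases.** Observed AUC = [p × AUC + F × 0.5]/(p + F), where F is the affected fraction of the cohort.
- Set A, high end: F = 0.14, prevalence 30% → 44%, AUC 0.85 → (0.255 + 0.070)/0.44 = 0.74. A true gap of 0.10 between two tools becomes 0.10 × 0.30/0.44 = 0.068.
- Set A, low end: F = 0.005, prevalence 50% → 50.5%, AUC 0.85 → 0.847. The gap becomes 0.099.
- Set B, s = 25%: the affected share of label-positives is c = 5.9/53.1 = 0.11 to 14.8/62.0 = 0.24, and AUC 0.80 → 0.80 − 0.30c = 0.77 to 0.73.

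**5. Effect if their muscle is 1 SD thicker than that of non-cases (a further assumption).** Their AUC against non-cases is Φ(−1/√2) = 0.24, so 0.80 → 0.80 − 0.56c = 0.74 to 0.67.

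**6. Scale.** The Hanley-McNeil standard error of an AUC of 0.80 with 47 cases and 71 non-cases is 0.044. The smallest Set B shift (0.033) is below it, and the largest in step 5 (0.133) is about three times it.

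**7. Could the ranking of tools change?** In step 4 every AUC moves toward 0.5 by the same factor, so the order is kept. A reversal needs a tool-specific assumption. For example, at c = 0.24 a mass tool at 0.80 falls to 0.67 under step 5, while a function tool at 0.75 that is unrelated to the extra muscle falls to 0.75 − 0.24 × 0.25 = 0.69. At c = 0.11 the same pair gives 0.74 and 0.72, and the order is kept.

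**The case against.** The strongest reply is that 7.3 applies a published consensus rule. Whether intended loss counts is then a choice of construct, and changing the main label would cost comparability. That stands, and it is why the published rule should be kept and reported.

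The second reply is that the premise is not documented. Nothing in the protocol says how many patients come from the diabetology-obesity service, how many are losing weight on purpose, or what their muscle is like. The gastrectomies in 7.2.1 are listed as a cause of poor absorption, with no link to intended loss. This stands too: the bias is a conditional risk, and at the low end it is negligible.

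Third, a reader might infer that these patients could never be identified afterwards. The documents do not support that. Service, BMI, reason for admission and MNA-SF item A, which ties reduced eating to appetite, digestive, chewing or swallowing problems, allow an imperfect flag. What they do not give is intent itself.

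Fourth, only a secondary analysis and a prevalence that is not a listed endpoint are exposed. The severe category in 7.3 has no analytic role, because the prevalence pools moderate and severe cases and 10.5 does not use severity. This limits the weight of the point but does not remove it.

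**Conclusion.** The gap is real and its consequence is conditional. As written, 7.3 can label intended weight loss with preserved muscle as undernutrition, and the plan has no item that shows how often this happens. The number affected is about 1 to 16 of 118 under Set A and up to 24 under the widest Set B assumptions. All of these rest on assumed service shares and frequencies of intended loss. The AUC effect runs from under 0.01 to about 0.11 (Set A, true AUC 0.85), and is larger only if these patients also have thicker muscle than other non-cases.

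Three stronger readings are tempting and not supported:
- That any loss above 5% is enough. The 5% limit applies within six months, more than 10% is needed beyond that, and an etiological criterion is required as well.
- That the prevalence will be inflated or the ranking of tools reversed. The first depends on unknown frequencies, the second on an added tool-specific assumption.
- That the primary result is compromised. The impedance-referenced accuracy, the intraclass correlations and N = 118 do not use this label.

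This is a cheap improvement to a secondary analysis.

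**What to change.** Add to 9.2 and the e-CRF one item, intended yes/no, for weight loss and for reduced intake, completed at inclusion. Pre-specify in 10.5.2 that the AUCs and the prevalence are reported twice: once with the published rule in 7.3 unchanged, and once with intended loss or intended intake reduction not counted toward the study label. In the second version a patient can still qualify through BMI, reduced muscle mass or the other etiological criteria.

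The cost is one e-CRF item, a sentence in 10.5.2 and one repeated secondary analysis. Intent is partly self-reported and a few mixed cases will need a judgement, best made without sight of the muscle measurements. The item should be collected prospectively, since intent is hard to recover after discharge. The change concerns the study label only and does not touch diagnosis or care on the ward.
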